5.10. Other Analyses

Assessments that were not completed or missed due to COVID-19 will be listed per visit.

6. CHANGES IN PLANNED ANALYSIS

There have been no changes to the initially planned analyses as of the finalization of this SAP.

7. DEFINITIONS AND CONVENTIONS FOR DATA HANDLING

7.1. Baseline Period

Baseline evaluations or events will be defined as evaluations or events that occur before the date and time of the first dose of study drug.

If the onset time of event or evaluation time or dosing time is missing or not collected, the following definitions will apply:

- Pre-treatment AEs will be defined as AEs with an onset date prior to but not including the day of the first dose of study drug
- Baseline evaluations (laboratory tests, ECOG PS and vital signs) will be defined as evaluations with a date on or prior to the day of first dose of study drug (for ECG, assessments on the day of first dose of study drug will not be included in baseline evaluation)

If there are multiple valid assessments, the assessment that is closest to the day (and time if collected) of the first dose of study drug will be used as the baseline in the analyses. If multiple assessments are collected on the same date (and time, if collected), the assessment with the latest database entry date (and time, if collected) will be considered as baseline.

7.2. Post-Baseline Period

To allow differentiation as to which study period an AE occurred, three categories are defined based upon onset date. AEs that have onset dates prior to the first dose of study drug are considered "prior." AEs with onset dates on or after the first dose of study drug and within 30 days following the last dose of study drug are considered "on-treatment" or equivalently "treatment emergent.". Events with onset dates more than 30 days after the last dose of study drug are considered "post-treatment." No "subtracting rule" will be applied when an AE occurs both pre-treatment and post-treatment with the same preferred term and grade. AE summary tables will be based on on-treatment AEs only. AEs with onset dates prior to the first dose of study drug as well as those after the last dose of study drug +30 days will be identified in the data listings.

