9. SAFETY EVALUATIONS

9.1. Adverse Events

An AE is defined as any untoward medical occurrence in a clinical study patient and does not necessarily have a causal relationship with the study drug. An AE can therefore be any unfavorable and unintended sign (including an abnormal finding), symptom, or disease temporally associated with the use of a study drug, whether or not related to the study drug. This includes any occurrence that is new in onset or aggravated in severity or frequency from the baseline condition, or abnormal results of diagnostic procedures, including laboratory test abnormalities. For this study, progression of the cancer under study is not considered an AE unless the Investigator deems it related to study drug.

All AEs will be collected from the time informed consent has been documented through 30 days after the last dose of any study drug (safety follow-up) or until the start of new antitumor therapy, whichever is earlier. Any untoward medical event that occurs after the safety follow-up is not considered an AE, unless the Investigator considers that the AE is related to the study drug.

Signs and symptoms of a preexisting disease should not be considered an AE, but should rather be considered baseline signs and symptoms. Clinically significant worsening of preexisting signs and symptoms is considered an AE.

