5.6.2.2. Adverse Events

An AE is any untoward medical condition that occurs in patients while participating in this clinical trial. AEs will be coded according to the MedDRA (the most up-to-date version at the time of analysis) terminology and the severity of the toxicities will be graded according to NCI CTCAE Version 5.0, where applicable.

A treatment-emergent AE (TEAE) is defined as an AE that is starting or worsening at the time of or after the first dose of study drug administration and within 30 days after the last dose of study drug, and does not necessarily have a causal relationship to the use of the study drug.

In this study, only TEAEs will be summarized. Note that all collected AEs, including TEAEs, will be presented in listings as described in Section 5.1.

The following summary tables will be generated:

1. Summary of AEs with the number and percentage of patients reporting AEs, serious AEs, grade ≥ 3 AEs, AEs leading to study drug discontinuation, interruption and dose reduction, and AEs with the outcome of death.
2. Summary of treatment-related AEs with the number and percentage of patients reporting AEs, serious AEs, grade ≥ 3 AEs, AEs leading to study drug discontinuation, interruption and dose reduction, and AEs with outcome of deaths.
3. Summary of AEs by worst CTC Grade (grade 1, 2, 3, 4, 5, any grade, Grade ≥ 3) presented by SOC and Preferred Term (PT).
4. Summary of TEAEs by worst CTC grade (Grade 1, 2, 3, 4, 5, any grade, Grade ≥ 3) presented by SOC and PT.
5. Grade ≥ 3 AEs by worst CTC Grade (grade 3, 4, 5, 3-5) presented by SOC and PT.
6. Grade ≥ 3 TEAEs by worst CTC Grade (grade 3, 4, 5, 3-5) presented by SOC and PT.
7. Summary of AEs leading to death by SOC and PT.
8. Summary of the most common AEs ($\geq 10\%$ incidence) and median time to first AE by SOC and PT.

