7.6. Other Data Handling Rules

Missing data will not be imputed in listings. The listings will only present the data recorded on the original Case Report Form.

If an AE has a completely missing onset date, then the AE will be considered a TEAE. A medication with a completely missing start date is considered a prior medication. A medication with a completely missing stop date is considered a concomitant medication.

If an AE or a medication has a partial missing start date or stop date, the following rules will be used to determine whether it is a TEAE, or a prior or concomitant medication.

Table 21: Partial Date Imputation Rule for TEAE or Medication

Partial Missing Start or Stop Date	Derived Start Date	Imputed Stop Date
Missing month and day, and the year is present	January 1 of that year or first dose date if the year is the same as the year of first dose date	December 31 of that year
Missing day, but year and month are present	First day of that month or first dose date if the year and month are the same as the year and month of first dose date	Last day of that month
Missing month, but year and day are present	Missing month derived as January or same as first dose month if the year is same as the year of first dose.	Missing month imputed as December

A date with a missing year will be considered as a completely missing date, and no imputation rule will be applied.

The rules described in [Table 21](#) is also used for determining the cycle of AE and concomitant medication. The derived date is used for determining TEAEs, the cycle of AE, and concomitant medication.

For medical history, pre-study surgery, prior radiotherapy, and prior systemic anticancer therapies, a partial missing start date will be imputed as below:

1. Missing year :no imputation, date left missing

2. Missing day and month : January 1 will be assigned to the missing fields.
3. Missing month only: Treat day as missing and replace both month and day with January 1.
4. Missing day only: Assign the first day of the month to the missing day.

Note: Additional rules for prior systemic anticancer therapies may apply as they pertain to checking for protocol violations

For medical history, pre-study surgery, prior radiotherapy, and prior systemic anticancer therapies, a partially missing stop date will be imputed as below:

1. Missing year : no imputation, date left missing
2. Month is missing and year is prior to year of first dose of study drug:impute 'December'.

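### SAP 5.6.2.2 and 7.2 define a treatment-emergent AE differently, so an AE that worsens after first dose can miss the AE summary tables; separately, one partial-date rule can place an on-treatment AE before first dose

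*SAP*

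**What the plan says.** SAP 5.6.2.2 defines a treatment-emergent AE (TEAE) as "an AE that is starting or worsening at the time of or after the first dose of study drug administration", up to 30 days after the last dose. It adds: "In this study, only TEAEs will be summarized".

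SAP 7.2 sets out study periods for AEs, where "three categories are defined based upon onset date". Under it, "AEs that have onset dates prior to the first dose of study drug are considered" prior. AEs with onset from first dose to 30 days after last dose are called on-treatment, which the section treats as the same thing as treatment emergent. It then says "AE summary tables will be based on on-treatment AEs only". Worsening is not mentioned. The section also says that no subtraction rule "will be applied when an AE occurs both pre-treatment and post-treatment with the same preferred term and grade".

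Protocol 9.1 makes pre-dose AEs possible: "All AEs will be collected from the time informed consent has been documented through 30 days after the last dose of any study drug".

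For partial dates, SAP 7.6 uses the derived date to decide TEAE status. Where the day and year are known but the month is not, Table 21 says: "Missing month derived as January or same as first dose month if the year is same as the year of first dose".

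**The concern.** The same term has two definitions in one SAP, and they differ on an AE that begins in screening (up to 28 days before first dose) and becomes more severe on futibatinib. It is a TEAE under 5.6.2.2. Under 7.2 it is a prior AE if its only onset date is before first dose. Section 7 holds the data-handling conventions, so a programmer could reasonably build the flag from it. Two programmers following this SAP could therefore produce different AE tables.

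The summaries of incidence, Grade 3 or higher events, serious events, events leading to discontinuation or dose modification, and events of special interest all rest on this flag. Any loss would run one way, towards under-reported toxicity.

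The Table 21 rule raises a second, independent question: whether a stated imputation can push an event that truly began on treatment to a date before first dose.

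**Working it through.** There is no plan figure to reproduce. The check compares the texts and then applies Table 21 to dates.

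**1. The two TEAE rules on one case.** First dose 15 June; Grade 1 onset 10 June; Grade 3 on 25 June.

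| How the worsening is recorded | SAP 5.6.2.2 | SAP 7.2 |
|---|---|---|
| One record, onset 10 June | TEAE | Prior, not tabulated |
| New record, onset 25 June | TEAE | On-treatment, tabulated |

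The rules disagree only in the first row. The loss needs two conditions: 7.2 governs, and the worsening stays under the pre-dose onset date. The documents state neither. Protocol 9.2.1 leaves AE recording to eCRF guidelines that are not among them.

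**2. Size of one omission.** Using the current protocol's cohort sizes: 1/100 = 1.0 point (A), 1/35 = 2.9 points (B), 1/20 = 5.0 points (C). The documents do not say how many screening AEs worsen after dosing, so no total follows.

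**3. Table 21, start-date rules.** First dose 15 June 2021, true onset 10 July 2021:

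- Month and day missing: derived date is the first-dose date, 15 June. TEAE.
- Day missing: derived date is 1 July. TEAE.
- Month missing: month set to June and day 10 kept, giving 10 June. Prior.

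A completely missing onset date is also a TEAE under SAP 7.6. So only the month-missing row can move an on-treatment onset before first dose. It does so when the year matches and the recorded day is earlier than the first-dose day.

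**4. How often, within that subset.** Assumptions: only the month is missing; true onset is on or after first dose in the same calendar year; onset is equally likely on each day of a window after dosing.

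For a first dose on 15 June and a 30-day window (15 June to 14 July), 14 of the 30 days fall on days 1 to 14 of July: 14/30 = 46.7% classed as prior. For a first dose on the 15th of any month of a 365-day year, 13 of 30 days are lost after six 31-day months, 14 of 30 after five shorter months, and 0 of 17 in December, where the window is cut at year end: (6×13 + 5×14 + 0)/(11×30 + 17) = 148/347 = 42.7%.

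Repeating this for every first-dose date and for windows of 30 to 365 days gives, by day of first dose:

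- day 1: 0%
- day 8: about 20%
- day 15: 42 to 43%
- day 22: 65 to 67%
- day 28: about 87%
- averaged over all first-dose dates: about 44 to 45%

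A further 0 to 2% give an impossible date, such as 31 June. The other two rows misclassify 0%. If the row used the later of the derived date and the first-dose date, its share classed as prior would also be 0%.

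**The case against.** A reader might infer that every pre-dose AE that worsens on drug drops out of every AE table. The documents do not support that.

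- SAP 5.6.2.2 is the section that specifies the AE tables, and it includes worsening. SAP 7.2 gives its purpose as placing AEs in study periods.
- Protocol 9.1 makes clinically significant worsening of pre-existing signs and symptoms an AE in its own right, and protocol section 6 treats signs and symptoms arising between consent and first dose as baseline findings. On that reading the worsening has its own record, dated after first dose, and both SAP sections count it.
- The no-subtraction sentence in 7.2 and the use in SAP 7.5 of a baseline grade for the same preferred term are both compatible with separate records.
- All AEs stay in the by-patient listings, with pre-dose onsets identified. Laboratory, ECG and ECOG worsening appears in shift tables (SAP 5.6.3, 5.6.6, 5.6.8). Dose interruptions, reductions and discontinuations are summarised with reasons (5.6.1.2), and on-treatment deaths are summarised separately (5.6.2.1).

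This stands as a limit on the consequence: the loss is possible, not certain. It does not remove the conflict, because agreement between the two definitions then depends on a recording convention that neither document states.

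On Table 21, the objection is that a known day and year with an unknown month is unusual, and that a derived pre-dose date may be correct because AEs are collected from consent. Both are fair. But the other rows and the completely-missing rule resolve the same doubt towards TEAE, and this row does not.

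**Conclusion.** SAP 5.6.2.2 and 7.2 conflict on worsening, and no precedence is given. An AE with pre-dose onset that worsens after dosing can be left out of the AE summary tables if 7.2 is programmed and the event is held as one record. The number affected cannot be derived from the documents; a figure such as 2% to 10% of patients would be an assumption without a source.

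The Table 21 defect is separate and does not depend on how worsening is recorded. The 44 to 45% applies only to true same-year on-treatment onsets with the month alone missing, under uniform dosing and onset dates. It is not a share of all AEs, and the absolute number is probably small.

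Both are worth correcting before the AE datasets are programmed: any error under-counts toxicity and the remedy is cheap.

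**What to change.** 1. **SAP 7.2:** replace the onset-only rule with the 5.6.2.2 definition: treatment emergent means onset, or worsening in grade, from first dose to 30 days after last dose.
2. **Dating of worsening:** state that a grade increase after first dose is identified by its own AE record or by a recorded grade-change date. Without this the revised 7.2 may not be programmable, since a single record with one onset date does not show when the grade rose.
3. **Table 21, month-missing row:** use the later of the derived date and the first-dose date, unless a recorded stop date precedes first dose. Where the recorded day does not exist in the first-dose month, say which date applies.

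The cost is a few SAP sentences and a small change to the AE derivation, plus a check that the eCRF captures grade changes as item 2 assumes. AE rates may come out slightly higher, because some events of uncertain timing will now count as treatment emergent.

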3.3.3. Safety Follow-Up Period and 30-Day Safety Follow-Up Visit

The Safety Follow-Up Period is the time from the date of last dose of study drug through the 30-Day Safety Follow-Up Visit, which must be performed 30 days (+7 days) following the last dose of study drug. If the patient starts new anticancer therapy within 30 days of the last dose of study drug, the 30-Day Safety Follow-Up Visit should be performed before the start of new anticancer therapy. Every effort should be made to perform the assessments outlined in the schedule of events. If the patient is unable to return to the study site, a follow-up phone call can

be made by the study site to collect any new safety information that occurred during the Safety Follow-up Period.

After the 30-Day Safety Follow-Up Visit (see below), patients who have not started treatment with a new anticancer therapy will be assessed for drug-related SAEs only.

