5.6.2.5. Serious Adverse Events

Serious adverse events (SAEs) will be summarized:

- Summary of SAEs by worst CTC Grade (grade 1, 2, 3, 4, 5, any grade, Grade ≥ 3) presented by SOC and PT
- Summary of treatment-related SAEs by worst CTC Grade (grade 1, 2, 3, 4, 5, any grade, Grade ≥ 3) presented by SOC and PT

A by-patient listing of SAEs will also be provided.

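### No SAP table counts Investigator-related SAEs or fatal AEs that start more than 30 days after the last dose; they reach only the listings

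*SAP*

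**What the plan says.** The SAP applies one window to all adverse-event tables. Section 4.1 makes the On-treatment Period, Day 1 to 30 days past the last dose, the default for safety analyses unless a section specifies otherwise. Section 5.6.2.2 defines a TEAE as starting or worsening from first dose "and within 30 days after the last dose of study drug, and does not necessarily have a causal relationship" to the drug, and adds: "In this study, only TEAEs will be summarized". Section 7.2 repeats the rule. "Events with onset dates more than 30 days after the last dose of study drug are considered" post-treatment, "AE summary tables will be based on on-treatment AEs only", and pre-dose AEs "as well as those after the last dose of study drug +30 days will be identified in the data listings".

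The tables that report drug-related or fatal harm are in 5.6.2.1 (on-treatment deaths), 5.6.2.2 item 2 (treatment-related AEs, with rows for serious and fatal ones), 5.6.2.2 item 7 (AEs leading to death) and 5.6.2.5 ("Summary of treatment-related SAEs by worst CTC Grade").

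The protocol treats late events by causality. Section 9.1 says an event after safety follow-up is not an AE "unless the Investigator considers that the AE is related to the study drug". Section 3.3.3 says that after the 30-day visit "patients who have not started treatment with a new anticancer therapy will be assessed for drug-related SAEs only". Section 9.4.2 requires prompt notification of a related SAE, including a death, learned of at any time after discharge from the study. Section 11.5.4 promises incidence summaries of all AEs, broken down by causal relationship among other things, with separate SAE summaries.

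**The concern.** For late events the protocol uses relatedness as the filter: unrelated ones are dropped and related ones are kept. The SAP filters on time alone. The two rules meet in the tables meant to show drug-related harm, and the late events left out there are the ones the protocol chose to retain. A reader of the treatment-related SAE table would have no sign that further related SAEs were recorded, and would have to assemble the count from by-patient listings.

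**Working it through.** The plan states no figure on this point, so the check is mainly a comparison of text.

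**1. Does any table escape the 30-day rule?** Section 4.1 permits exceptions where specified. None of the relevant tables specifies one.

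| SAP table | Window stated in its own section | Related event, onset day 31 or later |
|---|---|---|
| 5.6.2.1 deaths | on-treatment only | death not counted |
| 5.6.2.2 item 2, treatment-related AEs | none, so TEAE rule applies | not counted |
| 5.6.2.2 item 7, AEs leading to death | none, so TEAE rule applies | not counted |
| 5.6.2.5 treatment-related SAEs | none, so 4.1 and 7.2 apply | not counted |

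SAP 7.4 acts the same way for AESI time-to-onset: an event starting after last dose + 30 days is censored at that point.

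**2. Are the events expected in the data?** Yes. Protocol 9.1 makes them AEs, Protocol 9.2.1 has all AEs entered in the eCRF, and SAP 7.2 provides for identifying them in listings.

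**3. Can the gap arise in routine conduct?** Protocol 3.3.3 schedules the safety visit at 30 days with a window of +7, so as late as 30 + 7 = 37 days after the last dose. The AE monitoring entry in Protocol Section 6 collects AEs until that visit is completed, unless new anticancer therapy starts first. An event with onset on days 31 to 37 can be collected on schedule and still fall outside every table.

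**4. Edge cases.** The cut-off is on AE onset. A related fatal AE that starts by day 30, with death later, stays in 5.6.2.2 items 2 and 7 and drops only out of the on-treatment death summary. An AE with a wholly missing onset date counts as a TEAE (SAP 7.6).

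**5. Is this a by-product of the amendment?** No. The SAP follows the earlier protocol version (115 patients, 60 in Cohort A), but that version's Sections 9.1 and 3.3.3 already had the same late-event provisions. The paragraph on late SAE notification in 9.4.2 is newer.

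**6. Size per patient.** Contribution of one patient = 1 / planned cohort size:

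- Cohort A: 1/100 = 1.0 percentage point (1/60 = 1.7 at the SAP's cohort size)
- Cohort B: 1/35 = 2.9 points
- Cohort C: 1/20 = 5.0 points

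These apply to a patient with no earlier related SAE inside the window.

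**The case against.** The strongest reply is that the window is the protocol's own basis. Its synopsis rests the safety assessment on TEAEs, and 11.5.4 ends its by-patient AE listings at the close of the Safety Follow-up Period. Section 9.1 settles when a late event is an AE, not which table it enters. This stands as a defence of the main analysis: a reader might infer that TEAE-only tables breach the protocol, and they do not. It does not explain why no table at all counts the late related events.

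Nothing is lost. All collected AEs are listed, SAEs have their own listing, and all deaths are listed, including those in survival follow-up. This also stands; what is missing is a count.

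A reader might infer that the treatment-related rates are biased downward. The documents do not support that. The tables estimate incidence in a declared risk window, and neither document sets lifetime drug-related harm as the target.

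A reader might also want late events added into a combined rate. After the safety visit only drug-related SAEs are assessed, only in patients without new anticancer therapy (3.3.3), and 9.4.2 does not oblige Investigators to look for SAEs actively. A combined figure would add a selective, open-ended numerator to a systematic 30-day one, with no defined period at risk. That objection is sound, so the count should stay separate.

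Finally, the size is hypothetical. Neither document gives an expected number of late related events or evidence of delayed toxicity with this drug.

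**Conclusion.** The point holds in a limited form. Investigator-related SAEs and fatal AEs with onset after last dose + 30 days are retained by the protocol, listed by the SAP and counted in no SAP table. The 30-day TEAE tables are sound as the main analysis.

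It would go too far to say that every late death disappears from the tables, since early-onset fatal AEs remain in 5.6.2.2 items 2 and 7, or that harm is concealed, since the listings show each case.

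The effect is 1.0, 2.9 or 5.0 percentage points of Cohort A, B or C per patient whose only related SAE starts late, assuming planned cohort sizes; the number of such patients is unknown and may be zero. A single related fatal AE starting on day 31 would leave the tabulated related deaths at zero. No efficacy result or decision rule is affected. It is a cheap improvement in how safety is reported.

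**What to change.** Keep the 30-day TEAE tables as they are. In SAP 7.2, 5.6.2.1, 5.6.2.2 (items 2 and 7) and 5.6.2.5, add a separate supplementary count, by cohort, of:

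- Investigator-related SAEs with onset more than 30 days after the last dose;
- Investigator-related fatal AEs or deaths with onset more than 30 days after the last dose.

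Label it a minimum count, because ascertainment after the safety visit is incomplete, and do not merge it into the 30-day incidence. The exception clause in SAP 4.1 already allows this, and no new data collection is needed.

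The cost is SAP wording plus one extra line or one small table. The count of related harm may look slightly less favourable.
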